## Clinical Investigational Plan

In general, data analysis will be performed based on the analysis population on a per subject basis. If more than 1 device has entered the subject's body, the data analysis may be summarized on a per device basis, as appropriate.

### 6.2.2 Secondary Endpoints

The following endpoints will be summarized using descriptive statistics for each access arm of the study.

Event rates at 30 days for all-cause mortality, cardiovascular mortality, disabling stroke, non-disabling stroke, life threatening bleeding requiring transfusion, and acute kidney injury requiring dialysis and composite of periprocedural encephalopathy/all stroke/and all TIA:

The count and proportion of subjects who experience each of above endpoints as adjudicated by the CEC through 30 days post implant will be summarized. Subjects in the analysis population defined in section 6.2.1.2 will be included in the analysis.

Event rates at one year for all-cause mortality, cardiovascular mortality and disabling stroke:

Kaplan-Meier survival analysis will be used to estimate the event rates of all cause mortality, cardiovascular mortality and disabling stroke at one year post implant. Subjects in the analysis population defined in section 6.2.1.2 will be included in the analysis. The index procedure (TAVI) day is considered Day 0. The time-to-event will be determined from the date of index procedure to the first occurrence of the event for subjects experiencing the event, or, for those subjects not experiencing the event, to the last date they are known to be free of the event (this usually will be the last follow-up, contact date, or death date).

Rate of moderate or severe aortic regurgitation at one year:

The count and proportion of subjects with moderate or severe aortic regurgitation at one year will be summarized.

Functional improvements in NYHA classification, 6 minute walk test and EOA will be compared at 30 days:

Changes of NYHA classification, 6 minute walk and EOA at 30 days from baseline will be summarized using descriptive statistics.

Acute device success:

The count and proportion of subjects with acute device success (see Section 4.3.2) will be summarized.

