#### 4.2 Study Design and Scope

This is a multicenter prospective, non-randomized, 2-arm investigational study without concurrent or matched controls, designed to assess the use of the Portico TF or Alternative Access Delivery System to place a Portico transcatheter aortic valve through an alternative access site, specifically subclavian/axillary or TAO.

A minimum of 45 subjects will undergo transcatheter aortic valve replacement (independent of valve size) via the Portico TF or Alternative Access Delivery System in each arm. A minimum of 45 implants will be accessed via the subclavian/axillary access site arm of the study and a minimum of 45 implants will be accessed via the TAO access site arm of the study. A maximum of 12 investigational sites with prior alternative access technique experience in Europe and will be trained to participate in the study. Enrollment is anticipated to be completed approximately 8 months from the date of first enrollment. Data will be collected at pre-procedure, peri-procedure and at discharge as well as at 30 days, 6 months and 1 year post implantation. All active subjects will be followed for 1 year.

Data from other prospective clinical trials of ALT access in similar patient populations outside of Europe may be included in the analysis and support the submission for CE Mark. CE Mark will be submitted for each access route after implantation and 30 day follow up are completed.

Although the study will not test a hypothesis, the primary endpoint event rate for each cohort will be presented within the context of the range of rates reported for alternative access delivery of transcatheter valves in the literature.

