##### 6.2.1.2 Analysis Population

All subjects who have received a Patient Information Sheet, and signed an Informed Consent Form and Data Protection Form will be considered enrolled in the study. However, the analysis population will be based on subjects who have provided signed Informed Consent Form and Data Protection Form and had the SJM TAVI delivery system enter his/her body. The anticipated dropout rate for this study population is expected to be low, as part of the selection criteria is subject compliance with all follow-up visits. Subjects that withdraw from the investigation or are lost to follow-up will not be replaced in the analysis dataset.

It is anticipated that there may be subjects who are enrolled in the study but are not included in the analysis population. There may be subjects who gave consent to participate in the study but did not satisfy the baseline inclusion exclusion criteria, these are considered screen failures. There may also be subjects who have enrolled in the study and started the procedure, but do not have the SJM TAVI delivery system enter his/her body and are procedural exclusions due to their anatomy, circumstances related to the procedure, or physician judgment; these are considered to be procedural exclusion subjects. Screen failure subjects and procedurally excluded subjects will not be part of the analysis population.

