**Clinical Investigational Plan****Appendix D: Definitions**

Cardiovascular Mortality (VARC2)	
Any 1 of the following criteria:
 
 
• Death due to proximate cardiac cause (e.g., myocardial infarction, cardiac tamponade, worsening heart failure)
 
• Death caused by non-coronary vascular conditions such as neurological events, pulmonary embolism, ruptured aortic aneurysm, dissecting aneurysm, or other vascular disease
 
• All procedure-related deaths, including those related to a complication of the procedure or treatment for a complication of the procedure
 
• All valve-related deaths including structural or nonstructural valve dysfunction or other valve-related adverse events
 
• Sudden or unwitnessed death
 
• Death of unknown cause
 

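### One-year cardiovascular mortality and disabling stroke are estimated by Kaplan-Meier with censoring at death, which overstates both slightly in expectation

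*Combined protocol and SAP*

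**What the plan says.** Section 6.2.2 gives one method for three 1-year endpoints: "Kaplan-Meier survival analysis will be used to estimate the event rates of all cause mortality, cardiovascular mortality and disabling stroke at one year". Time runs from the index procedure to the first event or, for subjects without the event, "to the last date they are known to be free of the event". A parenthesis explains that date: "this usually will be the last follow-up, contact date, or death date".

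The death date cannot be a censoring date for all-cause mortality, where death is the event. Its place in that list therefore bears only on the other two endpoints. A non-cardiovascular death is censored in the cardiovascular mortality curve, and a death without prior disabling stroke is censored in the stroke curve.

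The same section reports the 30-day versions of these three endpoints as counts and proportions of the analysis population, so subjects who die stay in the denominator. The documents nowhere mention competing risks or cumulative incidence.

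**The concern.** An event rate at 1 year in a single-arm safety summary is naturally read as the share of treated subjects who had the event by then. Censoring at death does not estimate that share. It treats a subject who has died as if still able to have the event later, at the same rate as those still under observation. Kaplan-Meier suits all-cause mortality because nothing competes with death.

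Two things are at stake. The 1-year rates of cardiovascular death and disabling stroke would tend to be reported somewhat high. Each would also measure a different quantity from the 30-day endpoint of the same name, so the two could not be read as one series. Competing deaths are plausible in this population, since section 4.4.1 requires high operable risk.

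**Working it through.** **Inputs from the documents.** Section 4.2 sets the arm size ("A minimum of 45 subjects will undergo transcatheter aortic valve replacement", in each arm) and the follow-up ("All active subjects will be followed for 1 year"). On dropout, section 6.2.1.2 says only "The anticipated dropout rate for this study population is expected to be low", with no figure; zero is used here. The plan gives no 1-year rate, so there is no stated figure to reproduce.

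**Assumed inputs.** One-year cumulative incidences: cardiovascular (CV) death 5-15%, non-cardiovascular (non-CV) death 2-10%, disabling stroke 2-5%, death without prior disabling stroke 5-25%.

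**Direction.** With no other loss, each event adds 1/n to the cumulative incidence. In one minus Kaplan-Meier (1 − KM) it adds the current Kaplan-Meier survival divided by the number at risk. That is also 1/n until a competing death occurs and more than 1/n afterwards. So 1 − KM is never below the cumulative incidence, and it is strictly above when at least one event of interest follows a competing death.

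**Small example, n = 45.** Two disabling strokes after six deaths: 1 − KM = 1 − (38/39)(37/38) = 2/39 = 5.13%, against 2/45 = 4.44%. If both strokes precede the deaths, both estimates are 4.44%.

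**Expected size.** Let p1 be the cumulative incidence of the event and p2 that of competing death. With constant cause-specific hazards,

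1 − KM = 1 − (1 − p1 − p2)^(p1/(p1 + p2)).

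For p1 = 10% and p2 = 5% this is 1 − 0.85^(2/3) = 10.27%. Selected results:

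| Event, p1 | Competing death, p2 | 1 − KM | Excess (points) |
|---|---|---|---|
| CV death 5% | 2% | 5.05% | 0.05 |
| CV death 10% | 2% | 10.10% | 0.10 |
| CV death 10% | 5% | 10.27% | 0.27 |
| CV death 10% | 10% | 10.56% | 0.56 |
| CV death 15% | 10% | 15.85% | 0.85 |
| Disabling stroke 2% | 5% | 2.05% | 0.05 |
| Disabling stroke 3% | 15% | 3.25% | 0.25 |
| Disabling stroke 5% | 20% | 5.59% | 0.59 |
| Disabling stroke 5% | 25% | 5.77% | 0.77 |

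Over the whole assumed grid the excess is 0.05 to 0.85 points for CV death (1-6% relative) and 0.05 to 0.77 points for disabling stroke (3-15% relative).

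**Against sampling error.** Simulation at n = 45, 20,000 runs, no dropout:

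| Event / competing death | Mean excess (points) | SD of the rate (points) | Runs with KM higher |
|---|---|---|---|
| CV 10% / non-CV 5% | 0.27 | 4.4 | 81% |
| CV 15% / non-CV 10% | 0.86 | 5.4 | 98% |
| Stroke 3% / death 15% | 0.26 | 2.5 | 69% |
| Stroke 5% / death 20% | 0.59 | 3.3 | 87% |

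**Timing.** If 75% of strokes occur before any death, with stroke at 3-5% and death at 10-20%, the stroke excess falls to 0.04-0.15 points.

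**The case against.** The strongest reply is that nothing decided in this study depends on these rates. Section 6.2.2 summarises them descriptively. The primary endpoint, the sample size (6.3) and the success statement (6.6) all rest on 30-day major vascular complications, and the CE Mark analysis in 6.5 is triggered by 30-day visits. One subject in 45 is 2.2 points, so even an excess of 0.85 points is about 0.38 of a subject. The Appendix D definition of cardiovascular death is broad: it includes "Death of unknown cause", for example, which leaves fewer deaths to compete with that endpoint. Section 4.4.2 also excludes subjects with a life expectancy under 1 year. All of this stands, and it fixes the severity as minor. It does not make the estimator the right one for the stated quantity.

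A reader might infer three stronger things that the documents do not support:

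- **That the reported rates will certainly be too high.** The bias is in expectation. It is zero in a dataset where every event of interest precedes every competing death.
- **That the reported components will fail to add up to all-cause mortality.** On assumed CV 10% and non-CV 5%, the two Kaplan-Meier figures would total 15.54% against 15.0%. But non-cardiovascular mortality is not an endpoint, so the plan presents no such sum.
- **That only non-cardiovascular death competes with both endpoints.** For disabling stroke, any death without a prior disabling stroke competes, cardiovascular death included.

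**Conclusion.** The point holds as a minor one. As written, section 6.2.2 applies to 1-year cardiovascular mortality and disabling stroke an estimator that is biased upward in expectation for the proportion of treated subjects with the event, and that does not match the 30-day proportions. All-cause mortality is unaffected.

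The size, about 0.05 to 0.85 points, rests on assumed 1-year rates, constant hazards and no dropout. Early events shrink it. In the simulated scenarios the sampling SD was about 2.5 to 5.4 points at 45 per arm, so the bias would not change how a single arm's result is read. The case for correcting it is that the direction is known and the correction is easy, not that the rates would mislead materially.

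**What to change.** In section 6.2.2, keep Kaplan-Meier for 1-year all-cause mortality. For the other two endpoints specify the Aalen-Johansen cumulative incidence at 1 year:

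- cardiovascular mortality, with non-cardiovascular death as the competing event;
- disabling stroke, with any death without prior disabling stroke as the competing event.

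Censor only at withdrawal, loss to follow-up or end of follow-up, and remove the death date from the censoring list for these two endpoints. Section 5.15 lists death among the reasons for withdrawal, so the text should say that withdrawal here means withdrawal while alive; otherwise deaths could still be censored. With no loss before 1 year, the result equals the simple proportion and matches the 30-day format.

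The cost is a sentence or two of plan text and standard software. No new data are needed: section 5.15 already requires the cause of death to be documented, and the Synopsis has the Clinical Events Committee adjudicate endpoint events.

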### 6.3 Sample Size

The sample size of 45 subjects for each access route is based on the desire to estimate the rate of 30-day vascular complication with a sufficient degree of precision. The rate of major vascular complications at 30 days in Portico TF EU study was 5.9%. The rate of major vascular complications reported for other TAVI valves at 30 days in a weighted meta-analysis of 3,519 patients from 16 studies ranged from 5.0% to 23.3%. The same meta-analysis calculated a major vascular complication pooled estimate 30-day rate of 11.9% (95% CI 8.6%-16.4%). Assuming an event rate of 5.9%, with 45 subjects, the exact 90% CI is (1.45%, 15.32%). Therefore, a sample size of 45 will result in the 90% confidence interval half-width of 9.42% and the 95% upper confidence limit is within the range reported in the literature

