### 6.4 Justification of Clinical Investigation Design

The Portico valve has demonstrated safety and favorable clinical results via TF access in the TF EU Portico Trial (n=222). The study will evaluate the safety of alternative access for the approved Portico transcatheter aortic and includes a primary safety endpoint of major vascular complications at 30 days. This endpoint is appropriate because vascular access is the only new aspect being investigated in this study and 30-days has been established by VARC2 as the appropriate time period to assess early safety events such as major vascular complications.

Numerous studies have demonstrated that vascular complication rates at 30 days with ALT access are similar to that of the TF approach and that survival at 1 and 2 years is similar between the subclavian and the TF approach. The sample size of 45 subjects is adequate to ensure that the rate of the primary endpoint, major vascular complications at 30 days, is consistent with the rate for Portico valves delivered by TF access as well as with rates reported in the literature.

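### Section 6.3 gives 9.42% as the half-width of its 90% confidence interval, but half of the stated interval is 6.94 points, and Section 6.4 draws more assurance from 45 subjects than that precision gives

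*Combined protocol and SAP*

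**What the plan says.** Section 6.3 rests the sample size on estimation: "The sample size of 45 subjects for each access route is based on the desire to estimate the rate of 30-day vascular complication" with adequate precision. The planning rate comes from the sponsor's transfemoral study: "The rate of major vascular complications at 30 days in Portico TF EU study was 5.9" per cent. From it the section derives an interval, "Assuming an event rate of 5.9%, with 45 subjects, the exact 90% CI is (1.45%, 15.32" per cent), and in the next sentence states that "a sample size of 45 will result in the 90% confidence interval half-width of 9.42" per cent and that "the 95% upper confidence limit is within the range reported in the literature". The literature rates it refers to "ranged from 5.0% to 23.3" per cent, with a pooled value of 11.9%.

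Section 6.4 goes further: "The sample size of 45 subjects is adequate to ensure that the rate of the primary endpoint" agrees both with the transfemoral rate for this valve and with published rates.

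Two other sections bear on the reading. Section 6.2.1.1 specifies an exact binomial 95% upper confidence limit for the primary endpoint. Section 6.6 states that there is no formal hypothesis and compares the primary result with 5% to 23.3%; it sets no rule for the upper limit.

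**The concern.** The interval and the half-width stand in adjacent sentences and do not agree. A reader who halves the printed interval gets a figure about 2.5 points smaller than the one stated. There is no hypothesis and no power calculation, so precision is the whole argument for 45 per arm, and the summary figure for it should be right.

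Section 6.4 turns that precision into a guarantee about the rate. A sample size determines how closely a rate is estimated. It cannot determine what the rate turns out to be, or that it matches an external value. Each access route is to be submitted for CE Mark on these 30-day data, so the plan should claim only what the data can show.

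**Working it through.** **Inputs.** From Section 6.3: n = 45 per arm, planning rate 5.9%, stated exact 90% interval 1.45% to 15.32%, stated half-width 9.42%, literature range 5.0% to 23.3%, pooled rate 11.9%. From Section 6.2.1.1: exact binomial 95% upper limit. I read this as one-sided, so it equals the upper end of the two-sided 90% interval, which is how Section 6.3 appears to use it.

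**Step 1: reproduce the plan's interval.** Expected events x = 45 × 0.059 = 2.655. The Clopper-Pearson limits are:

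- lower = 5th percentile of Beta(x, n − x + 1) = Beta(2.655, 43.345) → 1.452%
- upper = 95th percentile of Beta(x + 1, n − x) = Beta(3.655, 42.345) → 15.322%

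This matches the stated interval.

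**Step 2: half-width and one-sided distances.**

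- Half-width: (15.32 − 1.45)/2 = 13.87/2 = 6.94 points
- Upper distance: 15.32 − 5.90 = 9.42 points
- Lower distance: 5.90 − 1.45 = 4.45 points

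The stated 9.42 is therefore the upper distance. No other usual calculation at 5.9% and n = 45 gives it:

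| Calculation | Points |
|---|---|
| Wald half-width, 90% / 95% | 5.78 / 6.88 |
| Wilson half-width, 90% / 95% | 6.14 / 7.46 |
| Exact 95% half-width | 8.07 |
| Exact 95% upper distance | 11.31 |

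**Step 3: what 45 subjects give at whole-number counts.** One-sided 95% exact upper limits, and their ratio to 5.9%:

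| Events | Observed rate | Upper limit | Limit ÷ 5.9% |
|---|---|---|---|
| 0 | 0% | 6.44% | 1.1 |
| 1 | 2.22% | 10.11% | 1.7 |
| 2 | 4.44% | 13.34% | 2.3 |
| 3 | 6.67% | 16.34% | 2.8 |
| 4 | 8.89% | 19.20% | 3.3 |
| 5 | 11.11% | 21.95% | 3.7 |
| 6 | 13.33% | 24.63% | 4.2 |

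At the assumed 5.9% itself the ratio is 15.32/5.9 = 2.6. Even with no events the limit (6.44%) lies above 5.9%.

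**Step 4: the literature range.** At the assumed rate the upper limit of 15.32% lies inside 5.0% to 23.3%, as Section 6.3 says. It stays at or below 23.3% up to 5 events and exceeds it at 6. The binomial probability of 6 or more events in 45 is 4.8% at a true rate of 5.9% and 45.0% at 11.9%.

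**The case against.** The strongest reply is that this is a wrong label on a correct number. The interval is right. For a safety endpoint analysed by its upper limit, the distance from the estimate to that limit is the more useful precision figure, and 9.42 is exactly that. The slip overstates the imprecision, so it does not flatter the design. No decision depends on it. All of this stands, and it is why the point is a correction of wording and not a challenge to the sample size. It does not remove the contradiction between the printed interval and the printed half-width.

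On Section 6.4, it can be said that agreement with 5.9% does not require excluding higher rates, and that the planning interval contains 5.9%. That is fair as to the word consistent. It does not rescue the claim that the sample size guarantees such agreement.

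Three stronger readings are tempting, and the documents do not support them.

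- *That the interval is invalid because 2.655 events cannot occur.* Putting the expected count into the exact formula is an ordinary planning approximation. The attainable neighbours, 2/45 (0.80% to 13.34%) and 3/45 (1.84% to 16.34%), bracket the stated interval and lead to the same conclusion.
- *That the statement about the literature range is false because the limit leaves the range at 6 events.* That sentence follows from the assumed 5.9% and is true there. Section 6.6 compares the result with the range, not the limit. Six events in 45 is 13.3%, which is inside it, so no criterion would be breached.
- *That 45 subjects can never exclude some fixed multiple of the transfemoral rate.* The multiple depends on the count: 1.1 at no events, 1.7 at one, 2.3 at two, 2.8 at three.

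**Conclusion.** Section 6.3 misstates the precision figure that supports 45 per arm. The half-width of its own interval is 6.94 points, not 9.42, and 9.42 is the distance from the assumed rate to the upper limit. The difference is 9.42 − 6.94 = 2.48 points, in the direction that understates the design's precision. The sample size, the interval and the analysis method are unaffected.

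Section 6.4 overstates what 45 subjects deliver. At the assumed rate the 95% upper limit is about 2.6 times the transfemoral rate. The trial will give an estimate with that precision; it cannot ensure agreement with 5.9%.

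The half-width result needs only the plan's printed limits. The ratio of 2.6 and the 6-event boundary assume that the 95% upper limit is one-sided. If it were the upper end of a two-sided 95% interval, the limit at the assumed rate would be 17.21%, and the range would be exceeded from 5 events (24.05%). The 45% probability holds only if the true rate is the pooled 11.9%, which is not the planning assumption in Section 6.3, although Section 14.0 uses that rate for its termination table. It describes a limitation, not an error in the plan.

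**What to change.** In Section 6.3, replace the half-width statement with: *half-width of 6.94 percentage points, with the upper limit 9.42 points above the assumed rate*. Make the next statement explicitly conditional: *at the assumed rate of 5.9%, the 95% upper limit of 15.32% lies within the literature range of 5.0% to 23.3%*.

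Optionally add the boundary: *the exact one-sided 95% upper limit is at or below 23.3% for up to 5 events in 45 (21.95%) and above it at 6 (24.63%); the probability of 6 or more events is 4.8% at a true rate of 5.9% and 45% at 11.9%*.

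In Section 6.4, replace the guarantee with the precision achieved: *at an event rate of 5.9%, 45 subjects give a 95% upper limit of 15.32%, about 2.6 times the transfemoral rate; the study estimates the rate with this precision and does not ensure that it agrees with the transfemoral rate*.

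The cost is wording in two sections. The number of subjects, endpoint, interval and analysis stay as they are. The one downside is that the plan's stated assurance becomes weaker.
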